### 8.2.2 Previously Noted Adverse Device Effects

Any ADE that is not identified in nature, severity, or is not listed below is considered unanticipated:

- Temporary upset may occur as a result of discontinued access to DISC-MA at the end of the study.
- Given that the study involves use of a smartphone application, there is the small possibility of unintended application outages.

## 8.3 Assessment of Adverse Events

The investigator will be alert to any complaints or adverse reactions that arise and will take appropriate steps to Reduce the impact of any event . Existing disclaimers that DISC-MA is not intended for crisis management will be presented in the ICF and at onboarding. AEs may be received/identified via:

- 1) Spontaneous participant self reports communicated outside of the app
- 2) Solicited participant self reports collected via the Week 2 and Week 4 survey
- 3) Upon review of select conversations/transcripts with Woebot

Upon learning of a potential safety event, all relevant trial data will be compiled by a designated member of the study team and shared with the investigator. All events which meet criteria for an AE/SAE/UAP/UADE/Device Deficiency will be recorded by the PI or designee on the appropriate electronic Case Report Form (eCRF) and will follow a predetermined safety protocol as outlined in a Safety Management Plan (SMP).

### 8.3.1 Time Frame

Collection of AEs and SAEs will begin at ICF signature, and will continue through EOS at Week 4. Identification of any collected AEs/SAEs from transcript or LDP reviews is anticipated to be completed no earlier than 1 month following the last patient visit and no longer than 4 months from the last patient visit or until all data has been monitored and query cleaned.

### 8.3.2 AE Severity

If possible, investigators should report event terms that reflect a single, unifying diagnosis rather than individual signs or symptoms (e.g., “influenza” instead of “coughing, body aches, fever;” and “anemia” rather than “low hemoglobin”). A corresponding severity grading is to be performed by the investigator based on his/her best medical judgment as follows:

- **Mild (Grade 1):** asymptomatic or mild symptoms; clinical or diagnostic observations only; intervention not indicated
- **Moderate (Grade 2):** minimal, local, or noninvasive intervention indicated; limited age-appropriate instrumental activities of daily living (ADL)

- **Severe (Grade 3):** medically significant but not immediately life-threatening; hospitalization or prolongation of hospitalization indicated; disabling; or limiting self-care ADL
- **Life-threatening (Grade 4):** life-threatening consequences; urgent intervention indicated
- **Fatal (Grade 5):** death related to an AE

### 8.3.3 AE Causality

An event's relatedness to the investigational device will be determined by the Principal Investigator and classified under the following causality ratings:

- **Non-related:** There is no evidence of any causal relationship.
- **Related:** There is clear evidence of a causal relationship between the device and event; all other explanations have been ruled out.

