**Adverse Device Effect (ADE):** Any adverse event related to the use of an investigational medical device. This includes any adverse event resulting from insufficiencies or inadequacies in the instructions for use, the deployment, the implantation, the installation, the operation, or any malfunction of the investigational medical device. This also includes any event that is a result of a use error or intentional misuse.

**Unanticipated Adverse Device Effect (UADE):** Any serious adverse effect on the health or safety, or any life-threatening problem or death caused by or associated with a device which was not previously identified in nature, severity or degree of incidence in the protocol, Instructions for Use, Summary of Previous Studies Document, or other sources of information for the investigational product. Additionally, a UADE is any other unanticipated serious problem associated with the investigational device that relates to the rights, safety, or welfare of subjects.

UADEs will include events meeting either A or B as stated below:

*A. Events meeting ALL of the following criteria:*

- Not included in the list of Anticipated Events (refer to protocol section 8.2.2)
- Related (possibly, probably, or definitely) to the investigational device per the site principal investigator
- Serious (meets any of the SAE criteria)

*B. Any other unanticipated serious problem associated with the investigational device that relates to the rights, safety, or welfare of participants.*

**Device Deficiencies:** Inadequacy of a medical device related to its identity, quality, durability, reliability, safety or performance, such as malfunction, misuse or use error and inadequate labeling. The reporting of a Device Deficiency is a Product Complaint.

**Product Complaints:** Any written, electronic, or oral communication that alleges deficiencies related to the identity, quality, durability, reliability, safety, effectiveness, or performance of a device after it is released for distribution.

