## 8.4 Documenting and Reporting AE and SAEs

Designated members of the study team will report any identified potential safety events to the investigator within one business day from awareness. The investigator should seek to obtain information required to make a determination of causality and must assess the relationship of the event to the study device and complete the AE/SAE eCRF. Relevant follow up information should be updated as collected.

Any event that the Sponsor-Investigator determines is/are reportable to the IRB will be reported within 5 working days from making that determination. If it should be determined that an event presents an unreasonable risk to all participants, the study or parts of the study presenting that risk will be terminated as soon as possible.

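### The two causality ratings in Section 8.3.3 leave inconclusive events without a category and conflict with the relatedness levels used in the UADE and UAP definitions

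*Combined protocol and SAP*

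**What the plan says.** Section 8.3.3 (AE Causality) has the Principal Investigator place each event in one of two categories. Non-related is defined as "There is no evidence of any causal relationship". Related is defined as "There is clear evidence of a causal relationship between the device and event; all other explanations have been ruled out". There is no third category and no rule for cases in between. Section 8.4 makes the judgement compulsory: the investigator "must assess the relationship of the event to the study device and complete the AE/SAE eCRF".

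Section 8.2.1 defines the events that depend on relatedness:

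- **UADE, lead definition:** it covers serious effects "caused by or associated with a device which was not previously identified in nature, severity or degree of incidence in the protocol" or other listed sources.
- **UADE, routes:** "UADEs will include events meeting either A or B as stated below". Criterion A requires the event to be unlisted, serious and "Related (possibly, probably, or definitely) to the investigational device per the site principal investigator". Route B is "Any other unanticipated serious problem associated with the investigational device that relates to the rights, safety, or welfare of participants" and does not refer to a rating.
- **UAP:** one of its conditions is met by an event that is related, or possibly related, to taking part in the research. That is wider than the device alone.
- **ADE:** the event must be related to use of the device. No levels are given.

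Section 10.3.1 lists the frequency of AEs, SAEs and UADEs as the exploratory safety measure. Section 10.3.2 mentions device relatedness inside a partly redacted list of examples and says that n(%) is given for each safety endpoint. Section 8.3 adds that recorded events "will follow a predetermined safety protocol as outlined in a Safety Management Plan (SMP"). That plan and the eCRF are not among the documents.

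**The concern.** The two definitions in 8.3.3 describe the ends of a range. One requires the absence of any evidence. The other requires clear evidence and the exclusion of every alternative. Many real events lie between them, and this trial can be expected to produce some. Everyone enters with PHQ-8 or GAD-7 above 4, so if mood or anxiety worsens during use, the underlying condition is an obvious competing explanation. The Week 2 and Week 4 safety surveys ask directly about changes in mental health and new suicidal thoughts. With a single arm, no control group can help with attribution, so the investigator's rating carries most of the information on whether the device contributed.

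Two things are at stake. The first is whether a serious, unlisted event with inconclusive evidence is recognised as a UADE under criterion A. The second is whether any summary of device relatedness could be reproduced by another rater working from the same protocol.

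**Working it through.** The documents give no figure on this point, so the check is a comparison of definitions, followed by arithmetic for scale only.

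**Step 1. Is the 8.3.3 scale exhaustive?** Take four states of evidence and apply each test as written.

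| Evidence linking event to device | 8.3.3 rating | Relatedness condition of UADE criterion A |
|---|---|---|
| None | Non-related | Not met |
| Some, alternatives still open | Neither | Met if judged possible or probable |
| Clear, but an alternative not excluded | Neither | Met if judged possible, probable or definite |
| Clear, every alternative excluded | Related | Met |

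The two middle rows have no 8.3.3 rating. Calling such an event Non-related contradicts the definition of that category, because there is some evidence. Calling it Related contradicts the requirement that alternatives have been excluded.

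**Step 2. Do the scales refer to the same judgement?** Section 8.3.3 names the Principal Investigator and criterion A the site principal investigator. The synopsis gives one site, so I read these as the same rater (an inference). Both concern the device. The UAP test concerns the research as a whole, so it overlaps with the device judgement without being identical to it.

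**Step 3. Consequence for UADEs.** All conditions of criterion A must hold, so relatedness is necessary. If a serious, unlisted event from the middle rows is entered as Non-related, criterion A fails on that entry, although the same investigator might regard the event as possibly related. Route B and the lead definition rest on association with the device and do not use the 8.3.3 rating, so either may still bring the event in. The UAP route may too, subject to its other conditions.

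**Step 4. Consequence for a relatedness summary.** Let *d* participants have an event that meets Related as written, let *k* others have only middle-row events, and let *N* be the denominator. The related proportion can lie anywhere from *d/N* to *(d + k)/N*, depending on the assignment. The documents give neither *d* nor *k*, and 10.3.2 states no denominator.

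For scale, assuming a participant denominator, each reassigned participant moves the percentage by 100/*N*:

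- *N* = 200 (target): 100/200 = 0.50 points
- *N* = 180: 100/180 = 0.56 points
- *N* = 220: 100/220 = 0.45 points

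The range 180 to 220 is an assumed plus or minus 10% around the approximate target. With *N* = 200, *d* = 0 and an assumed *k* of 1, 5 or 10, the upper end would be 1/200 = 0.5%, 5/200 = 2.5% or 10/200 = 5.0%, against 0% at the lower end. If the denominator were recorded events, these figures would not apply, since the number of events is unknown. If *k* = 0, the range closes and the effect is zero.

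**Step 5. What does not use the rating.** The hold rule in Section 7 looks at how many AEs occur and how severe they are. The discontinuation criterion for SAEs in 5.3 uses grade. AE and SAE totals do not require relatedness. The WAI endpoint is separate.

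**The case against.** A two-level scale is a permissible choice, and one investigator at one site may apply it consistently. Section 8.4 has the investigator seek the information needed to judge causality, and Section 8.6 requires the sponsor to supply the Safety Assessment Committee with data good enough to confirm that judgement. The Safety Management Plan or the eCRF may hold guidance that cannot be seen here. The analyses are descriptive, safety is exploratory, and the protocol rates overall risk as low.

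These points limit the consequence but do not remove the conflict. Guidance elsewhere would still leave 8.2.1 and 8.3.3 at odds within the protocol.

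A reader might also infer four stronger things, which the documents do not support:

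- **That inconclusive events will be assigned arbitrarily.** The documents show only that the assignment is undefined and left to the investigator.
- **That device relatedness is a planned n(%) endpoint.** Section 10.3.1 does not list it. It appears in 10.3.2 as an example in a partly redacted sentence, so an n(%) table is plausible but not established.
- **That the count of related AEs will be too low.** The possible and probable levels belong to criterion A, which covers only serious, unlisted events. The ADE definition sets no levels, so the criterion A threshold is not the benchmark for every AE. Nor is it known how inconclusive events would be rated.
- **That serious inconclusive events will be lost.** Route B, the lead UADE definition and the UAP route all remain open.

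**Conclusion.** The point holds as an internal inconsistency. The 8.3.3 ratings are not exhaustive, they conflict with UADE criterion A, and they do not align with the UAP test. Followed literally, they leave inconclusive events without a rating and can keep a serious, unlisted, possibly related event out of criterion A.

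Confidence is high for the mismatch in wording and low for any numerical effect, whose size and direction cannot be derived. The figure of 0.45 to 0.56 points per participant rests on an assumed participant denominator and an assumed range around the target. It is not an estimate of bias. The point is worth correcting because the change is specific and cheap and improves safety classification. It does not threaten the study's primary aim.

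**What to change.** Reconcile the UADE and UAP definitions in 8.2.1 with the causality ratings in 8.3.3 before any safety table is produced. There are two workable forms:

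- one exhaustive causality scale that includes possible and probable levels and feeds the ADE, UADE and UAP determinations; or
- two ratings, reworded so that every event fits exactly one, with an explicit rule that maps the possible and probable levels to them.

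In either form, keep the UAP question about the research distinct from the question about the device. State which levels count as related in any device-relatedness table, and whether its denominator is participants or events. Align the eCRF and the Safety Management Plan if they repeat 8.3.3, and re-rate events already classified.

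The cost is an IRB-approved amendment under Section 14, possibly one eCRF field, and the work of re-rating. The reported number of related events may change. No visit, treatment or sample size is affected.

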### 8.3.3 AE Outcomes

The Investigator should document the outcome of AE and SAEs as:

- **Resolved**
- **Resolved with sequelae / chronic condition, no resolution expected**
- **Ongoing**
- **Death**
- **Ongoing at time of death**
- **Unknown**

## 8.4 Documenting and Reporting AE and SAEs

Designated members of the study team will report any identified potential safety events to the investigator within one business day from awareness. The investigator should seek to obtain information required to make a determination of causality and must assess the relationship of the event to the study device and complete the AE/SAE eCRF. Relevant follow up information should be updated as collected.

Any event that the Sponsor-Investigator determines is/are reportable to the IRB will be reported within 5 working days from making that determination. If it should be determined that an event presents an unreasonable risk to all participants, the study or parts of the study presenting that risk will be terminated as soon as possible.

## 8.5 Safety Monitoring

### 8.5.1 Safety Procedures At Screening

At screening, study participants will be asked to self-report on recent suicidal thoughts including current suicidal ideation with plan and/or intent as well as attempts in the past 12 months. Responses are not monitored in real time. Participants who endorse having a current suicidal plan or intent or an attempt in the past 12 months will be excluded from the study. Participants will be notified that:

- They may benefit from a level of care beyond the scope of the study and investigational treatment.
- They should call 9-1-1 or go to their local emergency room and reach out to someone they trust and can help them stay safe if they feel they are in crisis or in need of medical attention.
- Will be electronically provided with a list of resources.

Participants who endorse **current** suicidal ideation with a plan **or** intent will also be notified that a member of the study team will attempt to follow-up with them. Three attempts will be made by the Study PI to contact participants by phone and/or email. The study team will make every effort to follow-up with the participant as soon as possible and no more than 3 business days following the initial report.

#### **8.5.2 Unscheduled Visits**

Study participants are able to initiate contact with the study team at anytime throughout the duration of the study. If the contact is attributable to safety reasons or if the study team learns about a suspected safety event at any time, then an Unscheduled Visit would ensue, wherein the qualified study personnel would attempt to follow-up with the participant, and if it is determined that they are in immediate risk for hurting themselves or others, appropriate steps would be taken as outlined in the study specific Safety Management Plan (SMP).

#### **8.5.3 Safety Event Solicited Self-Report Survey**

[figure not shown]
Study participants will be asked to self-report on potential safety events at the Week 2 and Week 4 timepoints. Questions will explicitly ask about changes in the past two weeks to their (1)medication and/or therapy, (2) mental and/or physical health, and (3) any new thoughts about ending their life including new intent/plan/or attempts. Information gathered through this survey will be used to inform the need for follow-up, AEs/SAEs/UAPs/UADEs/Device Deficiencies/UADE determination, and resolution.

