#### 3.1 Description of Trial Design

This study is a single arm pilot trial aimed at exploring and informing precision interventions within the Woebot for Mood and Anxiety investigational device. Study participation is up to 7 weeks in total, including a 2 week screening/baseline phase, followed by a 4 week active intervention phase, and 1 week to complete the final study survey.

Participants will be recruited and enrolled into the study by Lindus Health. All remaining data collection and study monitoring will be managed through the Citrus decentralized trial platform managed by Lindus Health and by designated Woebot Health study personnel.

Self-report survey assessments will be administered to all participants at Screening/Baseline, Week 1, Week 2, and Week 4. Members of the study team may contact participants through the Citrus platform via phone/sms and/or email to remind participants to complete study activities.

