#### **8.5.4 Language Detection Protocol (LDP)**

In addition to the onboarding screens re-stating that Woebot is not a crisis service, DISC-MA has a Language Detection Protocol (LDP), developed by Woebot Health. The purpose of the LDP is to detect potentially concerning topics within participant-input free-text and will be enacted for all participants in the study. Upon detection of any concerning topics, LDP initiates a conversation to remind the participant of the application's limitations of services and offer a resource list which includes readily accessible support channels. If a possible mention of concerning topics is detected, the participant is reminded of the limitations of services (which they will have already seen in both the informed consent and well as Woebot's onboarding screens) as well as offered a list of external-to-application resources, specifically contact information, that have been curated in consultation with suicide prevention experts. This resource list includes emergency contact phone numbers, and suicide ideation and domestic violence hotline information.

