## 8.6 Safety Assessment Committee (SAC)

The SAC is the formal WH committee charged with responsibility for the review and evaluation of previous as well as accumulating data from clinical studies of WH devices, to assess safety, perform signal confirmation and risk assessment, assess the risk-benefit associated with study continuation, efficacy and other trial conduct issues such as scientific merit, and to develop recommendations so as to ensure safety across studies and minimize risk for subjects. The SAC members will include the following individuals:

1. Independent Medical Safety Expert, who will serve as the SAC Chair;
2. A Clinical Development Lead;
3. a Medical Lead;
4. a Regulatory Lead;
5. a Device Vigilance Lead

Validated, accurate and interpretable data are to be provided to the SAC, as requested. Data files to be used for SAC analyses will undergo established data review/QC procedures to the extent possible and critical fields will be identified. The Sponsor must ensure that data is of sufficient quality to support the performance of safety surveillance and confirm the assessment of causality associated with the event(s), the associated WH application and confirmation of reportability.

The SAC will determine whether any missing data will significantly impact the safety assessment and will direct the necessary actions to address missing data.

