## 10.3 Safety Endpoints

### 10.3.1 Aims and Endpoints

The safety profile of DISC-MA will be investigated as an exploratory aim and measured through:

- Frequency of AE/SAE/UADEs
  - Spontaneous participant report of safety events that are determined to be an AE/SAE/UADE
  - Direct participant self-report of safety events at the Week 2 and Week 4 survey that are determined to be an AE/SAE/UADE
  - Transcript reviews that detect safety events and are determined to be an AE/SAE/UADE

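### The safety surveys look back a fixed two weeks but may each be answered up to 6 days late within window, so up to 6 days of device use may not be asked about

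*Combined protocol and SAP*

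**What the plan says.** Section 8.3.1 sets a continuous collection period: "Collection of AEs and SAEs will begin at ICF signature, and will continue through EOS at Week 4". Section 8.3 lists three ways in which events may come to light. They are spontaneous reports from participants, review of selected conversations with the app, and "Solicited participant self reports collected via the Week 2 and Week 4 survey". Only the last asks the participant a question.

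Section 8.5.3 describes the survey: "Questions will explicitly ask about changes in the past two weeks to their" medication or therapy and mental or physical health, together with any new suicidal thoughts, plans or attempts. Table 1 places the Week 2 survey at Day 14 with a window of +6 days and the Week 4 survey at Day 28 with a window of +6 days. Section 3.1 also plans a further week for completing the final survey.

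Safety is reported descriptively. Section 10.3.1 states: "The safety profile of DISC-MA will be investigated as an exploratory aim". Section 10.3.2 plans n(%) for each safety endpoint.

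**The concern.** A two-week look-back fits surveys given exactly on Days 14 and 28. The windows permit surveys that are anywhere from 8 days (Days 20 and 28) to 20 days (Days 14 and 34) apart, and they permit the first survey to fall as late as Day 20. The look-back does not stretch to match. Which days a participant is asked about therefore depends on when that participant answers, even when everyone follows the protocol.

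A late Week 2 survey leaves the first days of exposure to the app unasked. A late Week 4 survey can leave a strip in the middle unasked. An event that began and ended on those days could go unreported. Because the survey is on file and in window, no missing-value count or deviation listing would reveal it.

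**Working it through.** The plan gives no figure of its own here, so this is day counting.

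**Inputs**
- Week 2 survey on Day 14 + a, with a from 0 to 6 (Table 1).
- Week 4 survey on Day 28 + b, with b from 0 to 6 (Table 1).
- Look-back of two weeks (Section 8.5.3), taken as 14 days including the survey day, with a sharp edge. This is an assumption.

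**Formula**
- The Week 2 survey covers Days 1 + a to 14 + a.
- The Week 4 survey covers Days 15 + b to 28 + b.
- Days missed at the start: a.
- Days missed in the middle: max(0, b − a).
- Total missed from Day 1 to the Week 4 survey: a + max(0, b − a) = max(a, b).

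**Results**

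| Week 2 / Week 4 survey day | Days not asked about | Number | Share of days to the Week 4 survey |
|---|---|---|---|
| 14 / 28 | none | 0 | 0 |
| 17 / 31 | 1–3 | 3 | 3/31 = 9.7% |
| 17 / 34 | 1–3 and 18–20 | 6 | 6/34 = 17.6% |
| 14 / 34 | 15–20 | 6 | 6/34 = 17.6% |
| 20 / 34 | 1–6 | 6 | 6/34 = 17.6% |
| 20 / 28 | 1–6 | 6 | 6/28 = 21.4% |

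The two gaps never add to 12, because the total is the larger delay and not the sum. Among the 7 × 7 = 49 permitted pairs of days, one leaves no gap and 13 leave 6 days. These are possibilities, not frequencies, since the documents give no distribution of delays.

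Every unasked day falls on or before Day 20, so it lies inside the four weeks of app access (Section 4.1). Counted against those 28 days, the gap is max(a, b)/28, at most 6/28 = 21.4%, whichever survey is late. The total number of days asked about is 28 − max(0, a − b). It falls below 28, to a minimum of 22, only when Week 2 is later in its window than Week 4. In the other pairs 28 days are asked about, but unless both surveys are on time some of them lie after Day 28 and earlier days are still skipped.

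**Sensitivity to the day count.** If the look-back is the 14 days before the survey day, the maximum is still 6 (Days 14–19 for surveys on Days 14 and 34). If it is the survey day plus the 14 days before it, the maximum is 5. On-time surveys leave no gap under any of the three readings.

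**Two related gaps.** A missed Week 2 survey leaves the Week 4 survey day minus 14 days unasked, which is 14 to 20 days. That is non-response, and other provisions partly address it. Days between the baseline survey and Day 1 are also unasked, although collection starts at consent. Those matter less for the safety profile of the device.

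**The case against.** The strongest reply is that this rests on a summary of the survey and not on the survey itself. The form is not in the documents, and two weeks may be shorthand for the nominal interval. The sentence also leaves unclear whether the look-back governs the suicidality item, which is the most serious one. Parts of the safety text are redacted in the public copy, and the Safety Management Plan is a separate document. All of this stands, and it limits how firmly the point can be put.

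Other routes can also catch events. On contact, Section 8.5.2 says: "Study participants are able to initiate contact with the study team at anytime throughout the duration of the study". The language detection protocol "will be enacted for all participants in the study", and selected transcripts are reviewed. A change that persists into the look-back may still be reported, so the exposure is mainly to short-lived events. But spontaneous contact depends on the participant raising the matter or the team otherwise learning of it. Language detection and transcript review see only what is said in the app, and Section 4.3 does not monitor engagement during the trial. These routes narrow the gap without closing it.

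Section 3.1 provides for reminders: "Members of the study team may contact participants through the Citrus platform via phone/sms and/or email to remind participants to complete study activities". They may shorten delays but are optional and leave the look-back as it is. Section 8.6 says: "The SAC will determine whether any missing data will significantly impact the safety assessment and will direct the necessary actions to address missing data". It could be argued that unasked days count as missing data. On a plain reading a completed in-window survey is not missing, so neither that provision nor the counts in Section 10.5 would be triggered.

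Finally, a look-back equal to the nominal visit interval is a coherent choice, and a longer or variable recall has its own cost. That is fair and bears on the choice of remedy. It does not make the fixed look-back match the windows.

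**Conclusion.** The point holds as a minor one. With every participant in window, 0 to 6 days from Day 1 to the Week 4 survey are not covered by either look-back as described. The maximum is 5 under the most generous day count. The figures are shares of days, not of events.

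The consequence is possible under-ascertainment of brief events, of unknown size, in an exploratory, descriptive, single-arm safety summary. The primary alliance endpoint is not touched. The conclusion assumes that the form asks what Section 8.5.3 says it asks and that participants treat two weeks as a firm limit. Confidence is medium for those reasons.

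**What to change.** In Section 8.5.3, anchor the Week 2 question to the date of consent. Anchor the Week 4 question to the last completed safety survey, or to consent if none was completed, and record the date of each event. This closes every in-window gap and also covers the days before Day 1.

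If uniform recall is preferred, a fixed three-week look-back with event dates also closes every in-window gap after Day 1. The shortest that works is 20 days: a Day 20 survey must reach back to Day 1, and a Day 34 survey must reach back to the day after Day 14 (34 − 14 = 20). This option does not reach consent, and after a missed Week 2 survey it still leaves the Week 4 survey day minus 21 days unasked, or 7 to 13 days.

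Neither option covers a missed Week 4 survey. Under the anchored question the days after the Week 2 survey then stay unasked: 8 to 14 days up to Day 28, or 14 to 20 up to Day 34.

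The cost is one phrase and one date field in an electronic survey, plus IRB approval, with no extra visit. The anchored question makes recall longer and variable:
- 8 to 20 days at Week 4 when Week 2 was completed.
- Up to 34 days at Week 2 for someone who consented on Day −14 (20 + 14, counting a Day 0).
- Up to 48 days at Week 4 if that person missed Week 2 (34 + 14).

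The three-week version holds recall at 21 days, but its look-backs can overlap, so event dates are needed to avoid counting an event twice.
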